## 4.2 Gender/Minority/Pediatric Inclusion for Research

Women and individuals of ethnic and racial minorities will be included in the study. Interval evaluations will occur to ensure women and individuals of ethnic and racial minorities are being enrolled onto the study. Processes to increase enrollment for this population will occur if they are found to be underrepresented. Pediatric patients will not be included in the study, but Multiple Myeloma is not a disease of individuals under the age of 18.

## 4.3 Strategies for Recruitment and Retention

Physicians, advanced practice practitioners or other supportive care staff will introduce the opportunity for clinical trial enrollment. We will collaborate with the SKCC's Recruitment Enhancement Service (RES), a dedicated recruitment resource nested within the SKCC's CRO that is available to all study teams. The goals of the RES are to reduce the burden of recruitment, to free up the time and resources of study teams, and to ensure teams meet recruitment goals on time. RES services include: (1) consulting with study teams to identify strategies for recruitment and retention of research participants; (2) searching the EHR to identify potential participants (e.g., searching by diagnostic labels and billing codes); (3) facilitating both paper and electronic contact of those individuals to invite their participation; and (4) enabling networking opportunities across Jefferson, its owned entities, and local community hospitals so that investigators can share recruitment resources. (5) Promoting studies via various mechanisms including social media. Overall, the RES model has successfully enrolled thousands of participants for studies, allowing them to meet their recruitment goals more quickly and easily. We will

collaborate with the SKCC's Recruitment Enhancement Service (RES) to query the EHR system to identify participants who are eligible for this study. We may also leverage their existing relationships with community organizations and local hospitals, expertise in traditional and social media, and in-house resources for promotion of studies. This will include individuals with an ICD-9-CM (or ICD-10-CM) diagnostic code at either an office visit or on their list of known chronic conditions.

Multiple contact methods will be obtained to maintain communication and follow up with participants. Extensive discussion of risks and possible benefits of study participation will be provided to participants and their families, if applicable. A consent form describing in detail the study procedures and risks will be given to the participant. Consent forms will be IRB-approved, and the participant is required to read and review the document or have the document read to him or her. The investigator or designee will explain the research study to the participant and answer any questions that may arise. The participant will sign the informed consent document prior to any study-related assessments or procedures. Participants will be given the opportunity to discuss the study with their surrogates or think about it prior to agreeing to participate. They may withdraw consent at any time throughout the course of the study. A copy of the signed informed consent document will be given to participants for their records. The rights and welfare of the participants will be protected by emphasizing to them that the quality of their clinical care will not be adversely affected if they decline to participate in this study. The consent process will be documented in the clinical or research record.

## **4.4 Participant Withdrawal**

### **4.4.1 Reasons for Withdrawal**

Participants are free to withdraw from participation in the study at any time upon request.

An investigator may terminate a study participant's participation in the study if:

- Any clinical adverse event (AE), laboratory abnormality, or other medical condition or situation occurs such that continued participation in the study would not be in the best interest of the participant.
- The participant meets an exclusion criterion (either newly developed or not previously recognized) that precludes further study participation.

### **4.4.2 Handling of Participant Withdrawals and Participant Discontinuation of Study Intervention**

Participants who withdraw or discontinue the study intervention early will continue to receive their treatment in the infusion center as per the standard of care. If a patient withdraws from study early, end of study visit (semi-structured qualitative interviews) will

---

be offered. If a participant withdraws or discontinues the study early, they may be replaced at the discretion of the sponsor and Principal Investigator.

#### **4.5 Premature Termination or Suspension of Study**

This study may be suspended or prematurely terminated if there is sufficient reasonable cause. Written notification, documenting the reason for study suspension or termination, will be provided by the suspending or terminating party to the investigator, Janssen Scientific Affairs, LLC, regulatory authorities. If the study is prematurely terminated or suspended, the principal investigator will promptly inform the IRB and will provide the reason(s) for the termination or suspension.

Circumstances that may warrant termination include, but are not limited to:

- Determination of unexpected, significant, or unacceptable risk to participants.
- Insufficient adherence to protocol requirements.
- Data that is not sufficiently complete and/or evaluable.
- Determination of futility.

### **5 Study Intervention**

#### **5.1 Study Product**

DARZALEX FASPRO (daratumumab and hyaluronidase-fihj) for subcutaneous (SC) administration

##### **5.1.1 Daratumumab SC Dosing:**

All daratumumab administrations will be in an outpatient or home setting. Subjects will receive pre-injection medications and post-injection medication as outlined in Sections 5.7.1 and 5.7.2, respectively.

Vital signs should be monitored extensively on Cycle 1 Day 1 before, and after the first administration of daratumumab. Patients will be monitored for 3 hours after the first subcutaneous injection as per institutional protocol. For all other administrations, vital signs should be measured before the start of injection and at the end of the injection. If the subject experiences any significant medical event, then the investigator should assess whether the subject should stay overnight for observation. If the subject has not experienced a significant medical event but is hospitalized overnight only for observation, then the hospitalization should not be reported as an SAE.

If an IRR develops, then the injection should be temporarily interrupted or slowed down. In the event of a life-threatening IRR (which may include pulmonary or cardiac events)

---

or anaphylactic reaction, daratumumab SC should be discontinued, and no additional daratumumab SC should be administered to the participant.

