**Description of Intervention:**

- 1) All participants included in the study will receive daratumumab subcutaneous injection therapy (fixed dose 1800mg). On study, participants will receive 2 cycles of daratumumab in the infusion center, followed by 4 cycles at home followed by 2 more cycles at the infusion center. At the beginning of each cycle, patient reported outcome surveys and quality of life surveys will be collected (EORTC-QLQ-30, CTSQ, COST, and OOCAT). During the infusion center phase, administration will be given by an infusion center nurse. During the home infusion phase of the study a home infusion nurse will administer darzalex-faspro. During home administration, specific details on barriers to maintaining adherence will be collected and described with descriptive analysis (i.e. issues with storage, delivery, disposal of medication).

**Study Duration:** 36 months

**Participant Participation Duration:** 10 months

**Estimated Time to Complete Enrollment:** 26 months

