## **4 Study Enrollment and Withdrawal**

### **4.1 Eligibility Criteria**

#### **4.1.1 Inclusion Criteria**

Individuals must meet all of the following inclusion criteria in order to be eligible to participate in the study:

1. Able to provide signed and dated informed consent form
2. Willing to comply with all study procedures and be available for the duration of the study
3. Male or female, aged greater than 18 years of age
4. Has a diagnosis of Multiple Myeloma
5. Is on the monthly phase of daratumumab (either IV or SubQ) based regimen (every 4 weeks) (either monotherapy or in combination with oral agents)
6. Is willing to receive daratumumab subcutaneous injections
7. Lives within the range of Jefferson Home Infusion Services

8. Patients are willing to allow home infusion company visit them and administer Darzalex-Faspro in the home.
9. Women of reproductive potential must use highly effective contraception
10. Men of reproductive potential must use highly effective contraception
11. Adequate bone marrow function: ANC >1,000, Platelet Count > 50,000
12. Adequate liver function: AST/ALT < 2.5 times ULN, Bilirubin <2 times ULN
13. Adequate renal function: CrCl ≥ 20mL/min for single agent SC daratumumab. For combination studies: with lenalidomide ≥ 30mL/min
14. English Speaking

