### **Daratumumab Administration – Subcutaneous**

[Daratumumab should be given according to product information:

<http://www.janssenlabels.com/package-insert/product-monograph/prescribing-information/DARZALEX+Faspro-pi.pdf>

Daratumumab (1800 mg) will be administered by SC injection by manual push over approximately 3 – 5 minutes in the abdominal subcutaneous tissues in the left/right locations, alternating between individual doses. The volume of the SC solution will be 15 mL for the 1800 mg dose. Reasons for continued observation on subsequent daratumumab injection may include but are not limited to the following: subjects with a higher risk of respiratory complications (e.g., subjects with mild asthma or subjects with COPD who have an FEV1 < 80% at screening or developed FEV1 < 80% during the study without any medical history), subjects with IRR with the first injection of study drug, subject with decreased condition on day of dosing compared to prior dosing day. The dose of daratumumab will remain constant throughout the study.

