## 6.2 Treatment Period

## Initial Visit (Visit 1, Day 1)

- Verify inclusion/exclusion criteria.
- Document any changes in Medical History, Concomitant Medications
- Perform and record physical exam findings.
- Document ECOG performance status
- Collect labs: CBC, CMP, SPEP, sFLC, Serum Immunoglobulins
- Document Current Multiple Myeloma Disease Status
- Complete the following surveys electronically (Surveys will be completed 3-5 days after the treatment day):
  - Cancer Treatment Satisfaction Survey
  - EORTC QLQ-C30
  - COST Survey
  - OOCAT Survey
- Administer DARZALEX FASPRO in the infusion center. No observation period needed.

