Appendix A: Schedule of Events

## Appendices

### Appendix A: Schedule of Events

#### Events Schedule: Patients already on Monthly Daratumumab

Schedule of events										
For patients transitioning from IV to Subcutaneous therapy										
Events	Screening	Infusion Center		Home Infusion			Infusion Center		End of Study Assessment	Notes
	Day -30 to 0	C1D1 (+/-3 days)	C2D1 (+/-3 days)	C3D1 (+/-3 days)	C4D1 (+/-3 days)	C5D1 (+/-3 days)	C6D1 (+/-3 days)	C7D1 (+/-3 days)	C8D1 (+/-3 days)	No later than 45 days after last treatment cycle
Administrative Procedures										
Informed consent	X									
Inclusion/exclusion criteria	X									
General medical history	X									
Prior/Concomitant Medications	X									
ECG	X									
Current Myeloma Disease status	X									
Schedule of events										
For patients transitioning from IV to Subcutaneous therapy										
Events	Screening	Infusion Center		Home Infusion			Infusion Center		End of Study Assessment	Notes

	Day -30 to 0	C1D1 (+/-3 days)	C2D1 (+/-3 days)	C3D1 (+/-3 days)	C4D1 (+/-3 days)	C5D1 (+/-3 days)	C6D1 (+/-3 days)	C7D1 (+/-3 days)	C8D1 (+/-3 days)	No later than 45 days after last treatment cycle	
Pregnancy Test (WOCBP)	X										
CBC	X	X	X	X	X	X	X	X	X		
CMP	X	X	X	X	X	X	X	X	X		
Serum Protein Electrophoresis	X	X	X	X	X	X	X	X	X		
Serum Free Light Chains	X	X	X	X	X	X	X	X	X		
Serum Immunoglobulins	X	X	X	X	X	X	X	X	X		
Hepatitis B (HBV) serology	X										If not previously tested, local testing for hepatitis B surface antigen (HBsAg), hepatitis B surface antibody (Anti-HBs), and hepatitis B core antibody (Anti-HBc) should be sent.
Schedule of events											
For patients transitioning from IV to Subcutaneous therapy											
Events	Screening	Infusion Center		Home Infusion				Infusion Center		End of Study Assessment	Notes

	Day -30 to 0	C1D1 (+/-3 days)	C2D1 (+/-3 days)	C3D1 (+/-3 days)	C4D1 (+/-3 days)	C5D1 (+/-3 days)	C6D1 (+/-3 days)	C7D1 (+/-3 days)	C8D1 (+/-3 days)	No later than 45 days after last treatment cycle	
HBV DNA testing	X										For subjects with serologic evidence of resolved HBV infection (i.e., positive Anti-HBs or positive Anti-HBc) at Screening, HBV DNA testing by PCR must be performed locally.
Survey Assessments											
Treatment Burden Questionnaire		X	X	X	X	X	X	X	X		
COST Survey		X	X	X	X	X	X	X	X		
E-PRO survey tool		X	X	X	X	X	X	X	X		

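### Section 5.1.1 requires 3 hours of monitoring after the first subcutaneous injection, but Visit 1 says no observation is needed and makes no exception for participants switching from IV

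*Combined protocol and SAP*

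**What the plan says.** Section 5.1.1 (Daratumumab SC Dosing) sets the monitoring rule: "Patients will be monitored for 3 hours after the first subcutaneous injection as per institutional protocol". The sentence before it reads: "Vital signs should be monitored extensively on Cycle 1 Day 1 before, and after the first administration of daratumumab".

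The Visit 1 list in Section 6.2 ends with: "Administer DARZALEX FASPRO in the infusion center. No observation period needed". It gives no exception and does not refer back to Section 5.1.1.

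Three other places show who receives that dose:

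- Inclusion criterion 5 in Section 4.1.1: "Is on the monthly phase of daratumumab (either IV or SubQ) based regimen (every 4 weeks". Criterion 6 then requires willingness to receive SC injections.
- The Description of Intervention in the Study Summary: "All participants included in the study will receive daratumumab subcutaneous injection therapy (fixed dose 1800mg".
- Appendix A, whose schedule table carries the line: "For patients transitioning from IV to Subcutaneous therapy".

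Section 5.3, on SC administration, deals with later doses: "Reasons for continued observation on subsequent daratumumab injection may include but are not limited to the following". One of the reasons it lists is "subjects with IRR with the first injection of study drug".

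**The concern.** For a participant who arrives on IV daratumumab and has never had the SC form, Visit 1 is the first SC injection. Section 5.1.1 asks for 3 hours of monitoring after that dose, and the visit list says none is needed.

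The Visit 1 list is also silent on other Section 5 requirements, such as vital signs and premedication. Silence sends the reader back to Section 5. On observation, however, the list makes a positive statement, and that statement differs from Section 5.1.1. Staff working from the list could let a participant leave straight after the injection.

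Other parts of the protocol depend on knowing whether a reaction occurred. Section 5.3 makes a reaction to the first injection a reason for observing later ones. Section 5.7.1 lets corticosteroid premedication be reconsidered if there is no major reaction over the first three doses. Section 8.1.4 lists infusion reactions of Grade 3 or higher as events of special interest. Under Section 15.5, omitting the monitoring would also be a protocol deviation, even though the visit list prompted it.

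**Working it through.** The conflict itself is a matter of text, and the plan gives no figure to reproduce. Arithmetic is needed only for its reach.

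**Step 1. Compare the instructions for the same dose.**

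| Source | Dose covered | Observation |
|---|---|---|
| Section 5.1.1 | First SC injection | 3 hours |
| Section 6.2, Visit 1 | Day 1 dose, infusion center | None needed, no exception |
| Section 5.3 | Later injections | For selected participants |

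By speaking of observation that continues at later injections, Section 5.3 presupposes observation at the first. It therefore agrees with Section 5.1.1 and not with Visit 1.

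**Step 2. Can Visit 1 be the first SC injection?** Yes. Section 4.1.1 admits patients on IV, the Study Summary gives everyone SC, and Appendix A names IV-to-SC switchers. Appendix A has no observation row or note that would settle the matter.

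**Step 3. Is the Visit 1 line specific to the first dose?** No. The infusion-center sentence is the same at all 4 center visits (Visits 1, 2, 7 and 8), and the statement on observation appears at all 8 dosing visits. It reads as a default line carried through the schedule. Visits 2, 7 and 8 are cited only to show the repetition; they do not conflict with the first-injection rule.

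**Step 4. What does *first* mean?** Two readings are open. Section 5.1.1 links the first administration of daratumumab to Cycle 1 Day 1, although every participant is already on daratumumab at entry, and Section 5.3 refers to the first injection of study drug. Both point toward first on study. The 3-hour sentence itself says only first SC injection, which may mean first ever.

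**Step 5. Reach.** Inputs: 20 participants (Section 3.2) and 8 cycles with one dose each (Section 6.2).

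- Planned doses: 20 × 8 = 160.
- First-ever reading: k / 160, where k is the number of participants with no earlier SC dose. The documents do not give k, so the whole range from 0 to 20 applies.

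| k | Doses affected | Observation time, 3 h × k |
|---|---|---|
| 0 | 0 / 160 = 0% | 0 h |
| 5 | 5 / 160 = 3.1% | 15 h |
| 10 | 10 / 160 = 6.3% | 30 h |
| 20 | 20 / 160 = 12.5% | 60 h |

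- First-on-study reading: 20 / 160 = 12.5%, one dose per participant, 60 h in total.

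Participants replaced under Section 4.4.2 are not counted.

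**The case against.** The strongest reply is that this is a narrow drafting mismatch with a findable answer. Section 5.1.1 is mandatory and specific to the first SC dose, while the Visit 1 line is a repeated default. Saying that observation is not needed does not forbid it, so a site that observes for 3 hours complies with both sections. Participants already on SC at entry are unaffected if *first* means first ever, and there may be no switchers at all. Other safeguards exist: the institutional protocol named in Section 5.1.1, premedication before every dose, exclusion of known allergy to the product's components, extensive vital signs on Cycle 1 Day 1, and a staffed infusion center.

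Most of this stands, and it limits the size of the problem. It does not remove the conflict. A site can comply with both sections only if staff notice Section 5.1.1 and set aside a line telling them the step is unnecessary. The institutional protocol may lead them to observe, but Visit 1 does not mention it. The other safeguards do not replace the 3 hours, because the protocol requires them in addition. The percentages in the working span zero to 12.5% because k is unknown; they bound the reach and do not estimate it.

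**Conclusion.** The concern holds. For any participant whose first SC injection falls at Visit 1, the protocol gives two incompatible statements about whether observation is required, and no section says which governs. The Visit 1 statement is wrong as written for those participants, provided that Section 5.1.1, which Section 5.3 supports, reflects the sponsor's intent.

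The reach is one infusion-center visit per affected participant: 0 to 20 participants on the first-ever reading, and all 20 on the first-on-study reading. That the conflict exists is certain from the text; how many participants it touches cannot be known from the documents. The four home doses and the sample-size calculation are unaffected, and no effect on the questionnaire endpoints is claimed. The point should be corrected because it concerns a safety instruction and the correction is easy.

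**What to change.** Make two edits.

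1. At Visit 1 in Section 6.2, replace the unqualified line with: *Participants receiving their first subcutaneous daratumumab dose are observed for 3 hours per Section 5.1.1; others need no observation period unless Section 5.3 applies.*
2. In Section 5.1.1, state that *first* means the participant's first-ever SC dose.

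If the sponsor means first on study, Section 5.1.1 should say that, and Visit 1 should read: *All participants are observed for 3 hours per Section 5.1.1.* If the sponsor instead intends no observation at Visit 1, Section 5.1.1 is the text to change, with the reason given.

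For consistency, the same reference to Section 5.3 could be added to the matching line at Visits 2 to 8. This is optional, since Section 5.3 is permissive and does not conflict with those visits.

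The cost is one sentence and one clause, with no change to data collection or analysis. The 3 hours per affected participant (0 to 60 hours in total) are already required by Section 5.1.1, so neither version of the two edits that keeps that rule adds a new requirement.

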## **5.2 Study Product Description**

### **5.2.1 Acquisition**

The FDA approved product daratumumab and hyaluronidase-fihj will be supplied by the manufacturer during the home infusion phase of the study. During the infusion center phase of the study, the product will be acquired by the pharmacy.

### **5.2.2 Formulation, Packaging, and Labeling**

Injection: 1,800 mg daratumumab and 30,000 units hyaluronidase per 15 mL (120 mg and 2,000 units/mL) solution in a single-dose vial.

DARZALEX FASPRO (daratumumab and hyaluronidase-fihj) injection is a sterile, preservative free, colorless to yellow, and clear to opalescent solution for subcutaneous use supplied as individually packaged single-dose vials providing 1,800 mg of daratumumab and 30,000 units of hyaluronidase per 15 mL (NDC 57894-503-01).

### **5.2.3 Product Storage and Stability**

Store DARZALEX FASPRO vials in a refrigerator at 2°C to 8°C (36°F to 46°F) in the original carton to protect from light. Do not freeze or shake.

Once ready for use, it should be removed from refrigeration and equilibrate to ambient temperature [15°C to 30°C (59°F to 86°F)]. Store the unpunctured vial at ambient temperature and ambient light for a maximum of 24 hours. Keep out of direct sunlight.

If the syringe containing DARZALEX FASPRO is not used immediately, store refrigerated at 2°C to 8°C (36°F to 46°F) for up to 24 hours and/or at room temperature at 15°C to 25°C (59°F to 77°F) for up to 12 hours under ambient light.

Discard if storage time exceeds these limits.

## **5.3 If stored in the refrigerator, allow the solution to come to room temperature before administration. Dosage, Preparation, and Administration**

### **Daratumumab – Subcutaneous**

Daratumumab SC will be provided as a fixed-dose (1800 mg), combination drug product containing rHuPH20 drug substance (2000 U/mL) and daratumumab drug substance (120 mg/mL) in a single vial.

### **Daratumumab Administration – Subcutaneous**

[Daratumumab should be given according to product information:

<http://www.janssenlabels.com/package-insert/product-monograph/prescribing-information/DARZALEX+Faspro-pi.pdf>

Daratumumab (1800 mg) will be administered by SC injection by manual push over approximately 3 – 5 minutes in the abdominal subcutaneous tissues in the left/right locations, alternating between individual doses. The volume of the SC solution will be 15 mL for the 1800 mg dose. Reasons for continued observation on subsequent daratumumab injection may include but are not limited to the following: subjects with a higher risk of respiratory complications (e.g., subjects with mild asthma or subjects with COPD who have an FEV1 < 80% at screening or developed FEV1 < 80% during the study without any medical history), subjects with IRR with the first injection of study drug, subject with decreased condition on day of dosing compared to prior dosing day. The dose of daratumumab will remain constant throughout the study.

